ARQ-151-212 Amendment 2.0 August 05, 2019	
Updated Inclusion Criteria, increasing allowable range of baseline BSA to 1.5% to 35%Updated Inclusion Criteria, decreasing acceptable history of AD to 4 months, and stable disease for the past 3 weeks with no significant flares in atopic dermatitis before screeningUpdated Exclusion Criteria, removing restriction on prior ARQ-151 exposureUpdated Exclusion Criteria, decreasing time since major surgery from 8 weeks to 4 weeksUpdated washout periods, decreasing washout from 2 weeks to 1 week for topical corticosteroids, topical products containing urea, sedating antihistamines, topical antibacterials, calcineurin inhibitors, and Eucrisa®

	
(crisaborole)
 
• Revised PK testing plan to include only trough PK sampling for all new subjects enrolled under this amendment• Updated number of sites to approximately 30• Revised efficacy analysis removing vIGA-AD analyses• Editorial and administrative changes throughout the protocol to clarify language and formatting to improve readability, removed Sponsor and Coordinating PI signature page to a separate standalone document.
--	--

4 SYNOPSIS

Compound:	ARQ-151 cream 0.05% and ARQ-151 cream 0.15%
IND	135681
Clinical Indication:	Atopic Dermatitis
Study Phase and Type:	Phase 2 proof of concept study of the safety and efficacy of ARQ-151 cream 0.05% and 0.15% administered QD in adolescent and adult subjects with atopic dermatitis
Study Objectives:	
• To assess the safety and efficacy of ARQ-151 cream 0.05% vs ARQ-151 cream 0.15% vs vehicle administered QD x 4 weeks to adolescent and adult subjects with mild to moderate atopic dermatitis.• To evaluate the systemic exposure and characterize the plasma pharmacokinetic (PK) profile of ARQ-151 cream 0.05% and 0.15% and its major N-oxide metabolite, in adolescent and adult subjects with mild to moderate atopic dermatitis.
Summary of Study Design:	This is a parallel group, double blind, vehicle-controlled study in which ARQ-151 cream 0.05% or ARQ-151 cream 0.15% or vehicle is applied QD x 4 weeks to adolescent and adult subjects with atopic dermatitis. A subset of subjects that consented under the previous amendment will have serial PK testing, while only trough PK sampling will be performed for all new subjects enrolled under this amendment.
Blinding:	This study is double blind and vehicle-controlled
Countries:	Canada and United States (for all subjects)
Number of sites:	Approximately 30 sites in the US and Canada
Study Population:	Subjects will be male and female adolescents (12-17 y/o) and adults (≥ 18 y/o). Subjects will have atopic dermatitis involvement with a vIGA-AD score of '2' (mild) or '3' (moderate) for study entry.
Inclusion Criteria	
1. Participants legally competent to sign and give informed consent or, in the case of adolescents, assent with consent of a parent(s) or legal guardian, as required by local laws.2. Males and females ages 12 years and older (inclusive) at the time of consent.3. Clinical diagnosis of active atopic dermatitis according to the criteria of Hanifin and Rajka (1980). Subjects must have at least 3 of the 4 basic features (1. Pruritus; 2. Typical morphology and distribution [flexural lichenification in adults and facial and extensor eruptions in infants and children]; 3. Chronic or chronically relapsing dermatitis; or 4. Personal or family history of atopy), in addition to at least 3 minor criteria.

	
 4. History of AD for at least 4 months as determined by the Investigator through subject interview. Stable disease for the past 3 weeks with no significant flares in atopic dermatitis before screening. 5. BSA involvement of at least 1.5% (excluding the scalp, palms, and soles) but no more than 35%, at Baseline (Visit 2). 6. vIGA-AD score of 'mild' ('2') or 'moderate' ('3') at Baseline (Visit 2). vIGA-AD is evaluated for the entire body except the scalp, palms, and soles. 7. Subject has an EASI score of ≥ 5 at Baseline (Visit 2). EASI is evaluated for the entire body except the scalp, palms, and soles. 8. Females of childbearing potential (FOCBP) must have a negative serum pregnancy test at Screening (Visit 1) and a negative urine pregnancy test at Baseline (Visit 2). In addition, sexually active FOCBP must agree to use at least one form of highly effective contraception throughout the duration of the trial and for one week after application of the last dose. Highly effective forms of contraception include: oral/implant/injectable/transdermal contraceptives, intrauterine device, and partner's vasectomy. If barrier methods are used (e.g., condom with spermicide, diaphragm with spermicide), then 2 forms of contraception are required in association with spermicide. The use of abstinence as a contraceptive measure is acceptable as long as this is a consistent part of a lifestyle choice and an acceptable backup method has been identified if the subject becomes sexually active. 9. Females of non-childbearing potential must either be pre-menarchal, or post-menopausal with spontaneous amenorrhea for at least 12 months (post-menopausal status should be confirmed with FSH testing) or have undergone surgical sterilization (permanent sterilization methods include hysterectomy, bilateral oophorectomy, hysteroscopic sterilization, bilateral tubal ligation or bilateral salpingectomy). 10. Subjects in good health as judged by the Investigator, based on medical history, physical examination, vital signs, 12-lead electrocardiogram (ECG), serum chemistry labs, hematology values, and urinalysis. 11. Subjects are considered reliable and capable of adhering to the Protocol and visit schedule, according to the judgment of the Investigator.
Exclusion Criteria	
 1. Subjects with any serious medical condition or clinically significant laboratory, ECG, vital signs, or physical examination abnormality that would prevent study participation or place the subject at significant risk, as judged by the Investigator

	
2. Subjects who cannot discontinue medications and treatments prior to the Baseline visit and during the study according to Excluded Medications and Treatments (Table 1).3. Subjects who have unstable AD or any consistent requirement for high potency topical steroids to manage AD signs or symptoms.4. Subjects who have significant active systemic or localized infection, including known actively infected AD, or have had any infection that required oral or intravenous administration of antibiotics, antifungal or antiviral agents within 14 days prior to Baseline (Visit 2).5. Subjects who are unwilling to refrain from using a tanning bed or other LEDs as well as outdoor tanning or excessive sun exposure for 4 weeks prior to Baseline (Visit 2) and during the study.6. Subjects with skin conditions other than AD that would interfere with evaluations of the effect of the study medication on AD, as determined by the Investigator. Subjects with any condition on the treatment area which, in the opinion of the Investigator, could confound efficacy measurements.7. Subject has a known or suspected allergy to ARQ-151 or to excipients in ARQ-151 crea [REDACTED] [REDACTED] [REDACTED]8. Subjects who cannot discontinue the use of strong P-450 cytochrome inhibitors e.g., indinavir, nelfinavir, ritonavir, clarithromycin, itraconazole, ketoconazole, nefazodone, saquinavir, suboxone and telithromycin for two weeks prior to the baseline visit and during the study period.9. Subjects who cannot discontinue the use of strong P-450 cytochrome inducers e.g., efavirenz, nevirapine, glucocorticoids, barbiturates (including phenobarbital), phenytoin, rifampin, and carbamazepine for two weeks prior to the Baseline (Visit 2) and during the study period.10. Subjects who have received oral roflumilast (Daxas®, Daliresp®) within the past 4 weeks.11. Known or suspected:
• severe renal insufficiency or moderate to severe liver impairment (Child-Pugh B or C)• history of chronic infectious disease (e.g., hepatitis B, hepatitis C, or human immunodeficiency virus (HIV))• within last 5 years, a history of severe depression, suicidal ideation12. Females who are pregnant, wishing to become pregnant during the study, or are breast-feeding.
--	---

	
 13. Subjects with a history of chronic alcohol or drug abuse within 6 months of initiation of study medication. 14. History of and/or concurrent condition of serious hypersensitivity (anaphylactic shock or anaphylactoid reaction) to PDE-4 inhibitors. 15. Current or a history of cancer within 5 years with the exception of fully treated skin basal cell carcinoma, cutaneous squamous cell carcinoma or carcinoma in situ of the cervix. 16. Subjects with a history of a major surgery within 4 weeks prior to Baseline (Visit 2) or has a major surgery planned during the study. 17. Subjects who are unable to communicate, read or understand the local language, or who display another condition, which in the Investigator's opinion, makes them unsuitable for clinical study participation. 18. Subjects that are family members of the clinical study site, clinical study staff, or sponsor, or family members of enrolled subjects.
Number of Subjects:	Approximately 90 to 105 subjects; randomized 1:1:1 to ARQ-151 cream 0.05% : ARQ-151 cream 0.15% : vehicle and stratified based on IGA score of '2' (mild) or '3' (moderate).
Duration of Participation for Subjects:	Screening (up to 4 weeks) + Treatment phase (4 weeks) for a total of approximately 8 weeks
Study Products:	
 • ARQ-151 will be supplied as a 0.05% emollient cream and a 0.15% emollient cream • Matching vehicle will contain only excipients of ARQ-151 cream
Planned Dose Level:	Subjects will receive ARQ-151 cream 0.05% QD or ARQ-151 cream 0.15% QD or matching vehicle QD to be applied to all AD affected areas and any newly appearing AD lesions that arise during the study, except the scalp. Subjects should maintain treatment of areas with study drug for the duration of the study regardless of whether treatable areas of AD clear prior to Week 4.
Safety Assessments:	
 • Safety will be monitored through local tolerability assessments, vital signs, safety labs, 12 lead ECGs and AEs. • After obtaining consent, all AEs and TEAEs should be collected. • The investigator, or designee, will perform local tolerability assessments at Baseline (Visit 2), and weeks 1, 2, and 4 (Visits 4, 5, and 7). Subjects will have vital signs measured at each study visit, except for the 24-hour PK sampling visits (Visit 3 and 6) for subjects who agree to serial PK samples collected during the study. Height will be collected at Visit 1 only (Screening).

	
• A limited physical exam (skin, lungs, and heart only) will be performed at Visit 1-Screening, Visit 2-Baseline and Visit 7-Day 29. An ECG will be obtained at Visit 1-Screening and Visit 7-Day 29. Blood and urine samples for routine safety laboratory tests (hematology, serum chemistry, and urinalysis) will be obtained at Visit 1-Screening, Visit 2-Baseline and Visit 7-Day 29. For all female subjects of childbearing potential, a urine pregnancy test will be administered at all clinic visits, except for the 24-hour PK sampling visits (Visit 3 and 6) for subjects who agree to serial PK samples collected during the study, and except for Visit 1 (Screening) where a serum pregnancy test will be performed. A negative pregnancy result is required for continued participation in the study, and results (of the urine pregnancy test) must be available prior to dispensing of study drug at study visits.• Safety will also be monitored by PHQ-8 and C-SSRS.
Safety Analysis:	
The following analyses will be performed; however, no formal inferential statistics will be done on safety assessments. Descriptive statistics will be calculated for quantitative safety data and frequency counts will be compiled for classification of qualitative safety data. All subjects who are randomized and receive at least one confirmed dose of study drug will be included in the safety population.
 
Adverse Events:
 
All adverse events (AEs) reported during the study will be recorded and classified based on MedDRA terminology. Treatment-emergent adverse events (TEAEs) are defined as those AEs with an onset on or after the time of the first study drug application, or AEs that started before but worsened after first drug application. All reported TEAEs will be summarized by the number of subjects reporting TEAEs, system organ class, preferred term, severity, relationship to study drug, and as local to the study drug administration site or as a non-local TEAE. When summarizing TEAEs by severity or relationship to study drug, each subject will be counted only once within a system organ class or a preferred term by using the event with the greatest severity or causality, respectively, within each category.
 
Serious adverse events (SAEs) will be summarized by the number of subjects reporting SAEs, system organ class, preferred term, severity, and relationship to study drug.
 
All information pertaining to AEs reported during the study will be listed by subject, detailing verbatim term given by the Investigator, preferred term, system organ class, start date, stop date, seriousness, severity, action taken regarding study drug, corrective treatment, outcome, and relationship to study drug. In addition, a list of subjects who prematurely discontinued from the study due to an adverse event

	
will also be provided.
 
Subset analysis by age group (adolescents and adults) will be conducted.
 
Medical History, Physical Examinations, Vital Signs, Safety Labs and ECGs:
 
Medical history will be listed by subject. Clinically significant physical examination parameters will be captured as adverse events.
 
Safety laboratory parameters and vital signs will be summarized at each visit using descriptive statistics or frequencies and percentages, as appropriate. Changes from baseline in laboratory values and vital signs will also be summarized by visit. In addition, changes from baseline in weight and laboratory values will be summarized using shift tables according to normal ranges.
 
For ECGs, interval measurements will be summarized by time point using descriptive statistics. Changes from screening in interval measures will also be summarized. Any ECG abnormalities not present at Baseline will be identified in a listing of ECG abnormalities.
 
Subset analysis by age group (adolescents and adults) will be conducted.

Efficacy Analysis	
The Primary Efficacy Endpoint will be defined as:
 
• Change from baseline in Eczema Area and Severity Index (EASI) Total Score at Week 4 
The Secondary Efficacy Endpoints will include:
 
• Percent change from baseline in EASI Total Score at each study visit• Change from baseline in EASI Total Score at Weeks 1 and 2• Achievement of a 75% or greater improvement in Eczema Area and Severity Index (EASI75) score from baseline to each study visit• Achievement of a 50% or greater improvement in Eczema Area and Severity Index (EASI50) score from baseline to each study visit• Change from baseline in BSA involvement at each study visit• Change from baseline in WI-NRS pruritus score at each study visit• Achievement of a \geq 4-point improvement from Baseline in WI-NRS pruritus score at each study visit for subjects with a Baseline WI-NRS \geq 4 
Subset analysis by age group (adolescents and adults) will be

	conducted.
Power and Sample Size	
There are approximately 90-105 subjects planned for this study. Approximately 30-35 subjects will receive ARQ-151 cream 0.05% QD; approximately 30-35 subjects will receive ARQ-151 cream 0.15% QD; approximately 30-35 subjects will receive vehicle QD.
 
A sample size of 27 per arm will provide at least 80% power to detect a difference in the mean change from baseline in EASI Total Score of 35% at week 4 (for each ARQ-151-treated group versus vehicle-treated group), assuming a pooled standard deviation of 40%, with a two-sided $\alpha = 0.05$. This is based on a 2-sample t-test. This includes P value adjustment for multiplicity using Bonferroni correction. With a 10-25% dropout rate, the sample size for the study would be increased to 30-35 subjects per arm (90-105 subjects total). Change from baseline in EASI Total Score at Week 4 is expected to provide more statistical power than percent change from baseline in EASI Total Score at this timepoint (which is a secondary endpoint) and has been chosen as the primary endpoint.

Pharmacokinetic Sample Collection:	
• = 
For all subjects enrolling under this amendment:
 
• A single pre-dose PK sample will be collected on Days 1 and 29 (trough). 
For a subset of subjects:
 
• Subjects who consented to optional collection of serial PK samples under the previous amendment will participate in serial PK sampling.

Statistical Analysis:	
Four analysis populations will be defined:
 
• Safety population will include all subjects who are enrolled and received at least one confirmed dose of study medication; this population will be defined separately for each cohort.• Intent-to-Treat (ITT) population will include all randomized subjects.• Per-Protocol (PP) Population will include all subjects who are in the safety population, were at least 80% compliant with study medication, and showed no other serious deviations from the study protocol.• PK population will include all subjects receiving the active drug with sufficient plasma concentrations of roflumilast to define a profile, as determined by the pharmacokineticist. 
Pharmacokinetics Assessment
 
Plasma levels of circulating roflumilast and its major N-oxide metabolite will be measured at the following time points:
 
• Prior to study drug application on Days 1 and 29• Pre-dose, 1, 2, 4, 6 and 24 hours post-dose administration on Days 1 and 15 (PK subset only for subjects enrolled under the previous amendment) 
Efficacy Assessment
 
Descriptive statistics for continuous variables will include mean, median, standard deviation, min, max. Descriptive statistics for categorical variables will include frequencies and percents. For missing data, a multiple imputation technique will be detailed in the SAP. The primary endpoint 'EASI CFB' will be analyzed with Mixed Model Repeated Measures (MMRM) analysis with subject as a random effect and vIGA-AD strata, visit, treatment, visit by treatment interaction as fixed effects and baseline as a covariate. The week 4 treatment group comparison will be provided using the appropriate contrast.
 
Continuous secondary efficacy analysis will be analyzed in the same manner as the primary endpoint.
 
Categorical variables (such as proportion with EASI50) will be analyzed using Cochran-Mantel-Haenszel test adjusting for vIGA-AD strata.

------------------------------	---

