- ^e Local tolerability assessments should be recorded prior to study drug application for the Investigator assessment of skin irritation (Berger and Bowman skin irritation score) and 10-15 minutes post-drug application for the subject's '0-3' burning/stinging assessment.
- ^f Photography of AD lesion(s) selected by the Investigator will be performed at some investigational sites. Photography will be optional. All efforts will be made to de-identify the subjects.
- ^g A urine pregnancy test will be administered to all females of child-bearing potential. A negative result is required for continued participation in the study, and results must be available prior to dispensing of study drug at each visit.
- ^h For the subset of subjects who enrolled under the previous amendment and agreed to the serial PK: on the first day of dosing, PK draws will be done pre-dose (within 1-hour) and at 1, 2, 4, 6 (all \pm 20 min) and 24 hours (\pm 2 hr) post-dose administration. On Day 15, PK draws will be taken at pre-dose (within 1-hour), 1, 2, 4, 6 (all \pm 20 min) and 24 hours (\pm 2 hr) post dose administration. For other subjects: PK draws will be collected at Days 1 and 29. The draws will be pre-dose, \leq 60 minutes before drug application in the clinic. Ensure study medication is not applied in the area where PK will be drawn.
Note: Day 2 and Day 16 visits for 24-hour PK collection only apply to the subset of subjects who agree to the serial PK.
- ⁱ Subjects to apply assigned IP in clinic at every visit.
- ^j Kits will be dispensed based on %BSA affected. See IP Handling Manual for details.
- ^k The entire kit should be weighed and recorded at every visit. See IP Handling Manual for details.
- ^l Compliance calculation is described in the IP Handling Manual
- ^m Any emergent AEs will be followed in the clinic for up to one month at the Investigator's discretion until resolved or otherwise judged as clinically stable.
- ⁿ On Day 29, no further IP will be applied or dispensed.
- ^o On Day 8, dispensing of IP is optional. Site should review IP kit to ensure sufficient IP is available until the next visit and only dispense additional IP if needed.

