9.10.2 Treatment Administration

At the randomization visit (Baseline visit), the study staff will demonstrate to the subject how to apply ARQ-151 cream or vehicle cream using the first tube from the kit that is assigned to the subject at randomization. Study site staff will be trained to ensure a unit dose (a pea size unit of ARQ-151 vehicle cream will cover approximately 1% BSA) is properly squeezed from the tube and applied to atopic dermatitis lesion(s) as a thin film and rubbed in using the index and middle finger, rubbing in thoroughly but gently, until the 'white' has disappeared. The subject will then practice squeezing a similar amount onto their index and middle finger and apply a thin film to other areas to be treated. The study staff will confirm that the subject's application technique is correct.

Re-training will be conducted at subsequent visits as needed (i.e., if the returned tube(s) weighs substantially different than the expected weight).

Subjects will be instructed to apply study medication once daily to all treatment areas identified by the investigator at Baseline using a Body Diagram (see [Appendix 1](#)).

Note:

- All subjects should apply medication each evening (except on clinic visit days) at least 15 minutes after showering or bathing (if they take an evening shower/bath) and then not wash areas where ARQ-151 cream or vehicle has been applied until at least 4 hours after study drug application and preferably not until the following morning. Study medication should be applied at least 20 minutes before going to bed.
- Subjects should maintain treatment of areas with study drug for the duration of the study regardless of whether treatable areas of AD clear prior to Day 29.
- New lesions that develop during the study should be treated (except scalp). An unscheduled visit is not required for starting treatment of new lesions.

Each study medication tube will be weighed prior to dispensing at the baseline visit or subsequent visits. Study medication tubes must be returned by subjects at each study visit, both empty and full, and will be weighed. If the subject's actual use is substantially different than the expected use for the subject's BSA (see IP Handling Plan), the subject will be retrained on the study drug application technique.

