9.10.3 Treatment Compliance

Study medication tubes will be weighed at each follow-up clinic visit.

Subjects will complete a daily diary recording the date and time of each dose applied, any missed doses, and a comment section should the subjects have a comment, e.g., record potential AEs. Site personnel will review the diaries and use the information to question the subject regarding compliance and AEs and then record appropriate information in source documents and complete Case Report Forms (CRFs). If a subject misses a dose, they should be instructed to return to the protocol study medication administration schedule (i.e. if subject forgets a dose they should wait until that evening and apply as usual).

A subject will be considered compliant with the dosing regimen if the subject applies at least 80% of the expected applications during the study drug application period and does not miss more than 3 consecutive doses.

Compliance will be assessed by review of the dosing diary. Weight of study medication applied will be measured for reporting purposes.

If the diary shows less than 80% of expected use, the subject is using too little study drug and retraining must be conducted and documented.

Compliance will be documented in source and in eCRF.

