10.3.2 Pharmacokinetics Assessment

PK draws will be performed as follows for all subjects at all sites:

- For the serial PK subset enrolled under the previous amendment: On the first day of dosing, PK draws will be done pre-dose and at 1, 2, 4, 6 and 24 hours post-dose administration. On Day 15, PK draws will be taken at pre-dose, 1, 2, 4, 6, and 24 hours post-dose administration
- For all subsequent subjects enrolled under this amendment: PK draws will be collected at Days 1 and 29. The single draw will be pre-dose drug application in the clinic.

Ensure study medication is not applied in the area where PK will be drawn.

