11.1.1 Pharmacokinetics Assessment

Plasma levels of circulating roflumilast and its major N-oxide metabolite will be measured at the following time points:

- Prior to study drug application on Days 1 and 29
- Pre-dose, 1, 2, 4, 6 hrs post dose on Days 1 and 15, and 24 hrs post dose on Days 2 and 16 (serial PK subgroup enrolled under previous amendment only)

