## 11 STUDY TREATMENT EXPOSURE AND TREATMENT COMPLIANCE

---

A summary of exposure related to ARQ-151 cream and the vehicle will be presented using the safety population. It will include descriptive statistics on the number of days treated, as well as the number of treatment applications, for each treatment group.

For each treatment, compliance will be calculated as follows:

$$\frac{\text{Number of treatment applications}}{\text{Number of expected treatment applications}} \times 100$$

Since the study treatment is applied once daily, the number of expected treatment applications is 28 for all subjects. Descriptive statistics for the compliance as well as the number of missed applications, subjects with  $< 80\%$  and  $\geq 80\%$  compliance will be presented by treatment. Furthermore, the incidence of subjects who missed more than 3 consecutive doses and compliant subjects will be presented by treatment.

A subject will be considered compliant with the dosing regimen if the subject applies at least 80% of the expected applications during the study drug application period and does not miss more than 3 consecutive doses.

Exposure and compliance, including compliance collected at each clinic visit, will be displayed in a listing of study treatment administration by subject, for each treatment. A listing of drug accountability including the tube number, dispensed and returned weight will also be provided.

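### The Day 29 PK sample is defined as a pre-dose trough, but most of the text has no application on Day 29, so its time after the last dose is uncontrolled

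*Protocol*

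**What the plan says.** Several places in the protocol define the Day 29 draw by reference to a following application:

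- Synopsis, Pharmacokinetic Sample Collection: "A single pre-dose PK sample will be collected on Days 1 and 29 (trough".
- Synopsis (Statistical Analysis) and Section 11.1.1: "Prior to study drug application on Days 1 and 29".
- Section 10.3.2: "The single draw will be pre-dose drug application in the clinic".
- Section 5, footnote h: for subjects outside the serial subset, the draw is at most 60 minutes before application in the clinic.

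Other places indicate that no such application takes place:

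- The flow chart in Section 5 marks clinic application at Baseline, Week 1 and Week 2, and leaves Week 4 blank.
- Section 5, footnote n: "On Day 29, no further IP will be applied or dispensed".
- Section 10.1.8 schedules the subject's post-application tolerability rating at Baseline and Weeks 1 and 2 only.
- SAP Section 11: "the number of expected treatment applications is 28 for all subjects".

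One place points the other way. Section 5, footnote i: "Subjects to apply assigned IP in clinic at every visit".

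On home use, Section 9.10.2 says: "All subjects should apply medication each evening (except on clinic visit days". It gives no clock time. Section 9.10.3 provides the raw timing data: "Subjects will complete a daily diary recording the date and time of each dose applied".

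**The concern.** A trough has meaning only in relation to a dose. If nothing is applied on Day 29, a site cannot follow the rule in footnote h, and no other visible rule says how long after the last application the blood should be drawn. Subjects who dose in the evening and attend at different hours would then give samples at different points in the dosing interval. Protocol Section 11.4 plans descriptive statistics at each time point and mentions no adjustment for time since application.

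What is at stake is the exposure objective, which Section 8.1.1 lists among the primary objectives. For subjects enrolled under Amendment 2.0 the Day 1 sample precedes any study dose, so Day 29 is their only on-treatment measurement. SAP Section 5.1 describes the serial subset as approximately 18 adults; if that is complete, all on-treatment adolescent data come from this sample.

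**Working it through.** **1. Does a Day 29 application exist?** The one stated figure that bears on this is the SAP's 28. Once-daily application on Days 1 to 28 gives 28, which reproduces the figure. Days 1 to 29, as footnote i implies when read literally, gives 29. The flow chart, footnote n, the tolerability schedule and the SAP count therefore agree with one another, and footnote i alone disagrees. The sampling text (synopsis, footnote h, Sections 10.3.2 and 11.1.1) presupposes an application that this group of passages excludes. This step needs no assumption.

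**2. Time since the last application.** With an evening dose on Day 28 at clock hour *d* and a Day 29 draw at clock hour *c*, elapsed time is T = 24 + c − d. The documents give neither *c* nor *d*. Assume *d* between 18:00 and 23:00 and *c* between 08:00 and 17:00:

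- shortest: 24 + 8 − 23 = 9 h
- longest: 24 + 17 − 18 = 23 h
- example: 20:00 dose and 10:00 draw, 24 + 10 − 20 = 14 h

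The spread between subjects is 23 − 9 = 14 h. A draw at 24 h would need a visit at the same evening hour as the Day 28 dose.

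**3. What that could do to the concentration.** No half-life is visible, and the sections on topical results and dose selection are blacked out, so this is only an illustration. Under mono-exponential decline with half-life *h*, the ratio to the 24-hour level is R = 2^((24 − T)/h).

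| Assumed half-life | T = 9 h | T = 12 h | T = 16 h | T = 23 h |
|---|---|---|---|---|
| 12 h | 2.38 | 2.00 | 1.59 | 1.06 |
| 24 h | 1.54 | 1.41 | 1.26 | 1.03 |
| 48 h | 1.24 | 1.19 | 1.12 | 1.01 |

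Over the assumed ranges R runs from 1.01 to 2.38.

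**4. Does the visit window change the direction?** The Week 4 visit may be up to 3 days early or late (Sections 5 and 10.4). If daily application continues until the visit, T is unaffected. If a subject stops after 28 applications and attends on Day 30, T = 48 + c − d, from 48 + 8 − 23 = 33 h to 48 + 17 − 18 = 47 h, and R falls below 1. The documents do not say which applies.

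**5. Serial subset, Days 2 and 16 (secondary).** Section 9.2 calls these clinic visits. Section 9.10.2 excepts clinic visit days from evening home use, and the flow chart marks no clinic application on either day. Read literally, that gives 28 − 2 = 26 applications, against the SAP's 28 for every subject, while footnote i has an application at every visit.

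**The case against.** The strongest reply is that this is a wording conflict with limited consequences. The documents say trough and never 24-hour trough. Clinic hours, half-life and the shape of the decline are all assumptions. PK analyses are placed in a separate document (SAP Section 1) and blood sampling in a separate manual (Protocol Section 11.4). Neither was available for this review, and either could set draw times or use actual times. The diary records when each dose was applied and is reviewed at Day 29. Cmax and AUC come from the serial subset on Days 1 and 15, and SAP Section 4.4 restricts the PK population to subjects with serial data. Nothing suggests that timing would differ between the randomised arms.

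Much of this stands. It limits the point to the interpretation of one descriptive summary and rules out any claim about its numerical size. It does not remove the contradiction in the protocol that sites follow, and no visible passage says that the last-application time and the draw time both reach the PK data. Even if footnote i prevailed, so that pre-dose became literally true, the interval from the previous evening's dose would still be uncontrolled.

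A reader might go further and infer that the Day 29 samples fall well under 24 hours after dosing and so overstate the 24-hour trough, by a factor of 1.2 to 2.0. The documents do not support that. The factor takes a single time point, 12 h, from a range that reaches 23 h, where the ratio is only 1.01 to 1.06. The direction can also reverse for a late visit after dosing has stopped.

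**Conclusion.** The definition of the Day 29 sample is wrong as written. Its labels and its 60-minute rule refer to an application that the flow chart, footnote n, Section 10.1.8 and the SAP's application count all exclude, and footnote i conflicts with them. The draw therefore falls at an uncontrolled and variable time after the last application, probably under 24 hours for a daytime visit. The 9-23 hour range rests on assumed clock times. The ratios of 1.01 to 2.38 rest further on assumed half-lives of 12-48 hours and mono-exponential decline. Neither the size nor the direction of any effect on reported exposure is established. The point matters because exposure is a primary objective. It does not touch the efficacy analyses.

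**What to change.** - Reconcile footnotes h, i and n in Section 5 with the synopsis and Sections 10.3.2 and 11.1.1, so that one statement governs Day 29.
- Drop the trough and pre-dose labels for the Day 29 sample.
- Carry the time of last application, already in the diary, and the time of the draw into the PK dataset.
- Summarise Day 29 concentrations by actual time since last application, and state this in the separate PK analysis document if it is not already there.
- For the serial subset, reconcile the flow chart, footnote i, Section 9.10.2 and SAP Section 11 on whether an application takes place on Days 2 and 16.

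The cost is a protocol clarification, possibly one or two time fields in the data transfer, and a few lines of PK analysis text. No change to the dose or the schedule is proposed, and this review takes no position on which application rule should stand.
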